A Hybrid Type-I Implementation-effectiveness research design will allow the research team, comprising investigators with expertise in intervention development, efficacy and effectiveness research, and implementation science, to simultaneously investigate the effectiveness of *SAH-C* in a military population while identifying any barriers to implementation that would need to be addressed before *SAH-C* could be successfully implemented on a larger scale. The study site for this proposed effort is Joint Base Lewis McChord, Washington.

The primary hypotheses are that those receiving *SAH-C* will evidence greater reductions in physical and psychological IPV, and greater increases in relationship satisfaction, relative to those receiving *Supportive Prevention* across the follow up time points.

(c) Specific Objectives.

AIM 1: To test the effectiveness of *SAH-C* for military couples on an installation, we will conduct a randomized trial comparing 10 sessions of *SAH-C* to 10 sessions of *Supportive Prevention (SP)* under representative conditions, with 140 couples who are at risk for the development of IPA (risk is established if at least one member of the couple reports at or below a score of 100 on the Dyadic Adjustment Scale (DAS), a cutoff score used to distinguish relationship distress, or they report the presence of psychological aggression in the past three months). This aim will be fulfilled by accomplishing the following subaims:

Subaim 1.1: To compare the frequency of physical IPA perpetration of both members of the couple across conditions as reported by service members and their collateral relationship partners at post-intervention and two 3-month follow ups.

Subaim 1.2: To compare the frequency of psychological IPA perpetration of both members of the couple across conditions as reported by service members and their collateral relationship partners at post-intervention and two 3-month follow ups.

Subaim 1.3: To compare relationship satisfaction across conditions as reported by service members and their collateral relationship partners at post-intervention and two 3-month follow ups.

AIM 2: To explore differences in compliance factors across conditions, we will compare session attendance.

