One strategy to bridge the implementation gap is to capitalize on both researchers' and stakeholders' knowledge to ensure fit between the intervention training, provider needs, and organizational context. Recently described by Curran and colleagues,⁴⁸ a hybrid Type I implementation-effectiveness research design allows for the conduct of a rigorous effectiveness trial while simultaneously investigating potential barriers and facilitators to implementation. This information can guide future refinements to the intervention to improve the fit between the intervention and the service setting and inform the selection or development of an appropriate implementation strategy. Hybrid research methodologies, by increasing the efficiency of the research necessary to facilitate implementation, can reduce the time between the identification of effective interventions and their introduction into service systems and settings. The proposed design will position the research team and its operational partners to rapidly act on findings to enhance the effectiveness or fit of *SAH-C* in military settings if needed, and to roll the intervention out more broadly if our findings warrant doing so.

(c) Outline of *SAH-C*

SAH-C derives from a unique fusion of interventions for trauma and IPA, integrating elements of cognitive processing therapy for PTSD,³⁹ couples therapy for PTSD,⁴⁰ and a cognitive behavioral intervention for IPA.⁴¹ *SAH-C* consists of 10 two-hour weekly sessions, led by a provider. This was the minimum length deemed necessary to incorporate components addressing the proposed IPA mechanisms and is consistent with the briefest IPA interventions.⁴² During each session, couples are provided assignments to practice skills together and to assist with the consolidation of material. A group couples format is used because group cohesion among clients appears to be associated with IPA prevention.⁴³ Group interventions also use less time and resources than individual-based interventions. In this psychoeducation intervention, the couples participating in the program are the learners. What follows is a brief outline of each of the 10 *SAH-C* sessions.

Session 1: Introduction and Welcoming

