In total, 28 intervention groups will be conducted (14 for each condition), with five couples per group. Please see Section 2.c. for an initial outline of the *SAH-C* intervention. The *SP* intervention, used in our prior trial, is based on the work of Jennings⁷⁶ and on Yalom's⁷⁷ primary therapeutic factors for group intervention. This intervention involves minimal facilitator-directed intervention beyond encouragement of a mutually supportive environment and focus on relationship issues. In *ST*, the provider will allow group members to set the session agenda and address themes and topics that spontaneously emerge in the group interaction. The provider will emphasize a collaborative group norm and refrain from using active skills-training interventions. The provider will be instructed to address the group as a whole rather than individuals, and use brief verbalizations and nonverbal gestures to stimulate vigorous and helpful group interactions. This intervention was chosen to examine the relative benefits of the cognitive and behavioral interventions used in *SAH-C*.

(d) Intervention Integrity

Intervention integrity for *SAH-C* will be monitored using the intervention integrity measures used during Phase 1, as outlined in Section D.2.5. The same procedure will be used to measure intervention integrity for the *SP* condition, utilizing the modified *SP* codes developed in our previous trial. A framework of adaptations and modifications to evidence-based interventions⁷⁸ will be used to complement the integrity measure and identify any adaptations that the trained psychoeducational facilitator makes within session to address potential challenges or participant needs. Intervention integrity and adaptation data will be examined as implementation outcomes and will also be integrated with qualitative data to understand challenges to delivering the intervention with an adequate level of integrity and perceptions of the effectiveness of any adaptations that are made.

(e) Additional Intervention and Early Termination

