Participants (service members and partners) will separately receive remuneration of a \$50 Visa Gift Card or a \$50 check sent to their address for completion of each assessment. Due to military compensation restrictions, and to ensure no conflict, if the service member is active duty, they may only be compensated if they fill out their surveys while on off-duty or on leave status.

(h) Intervention after Completion of Trial

Following the completion of the final assessment, all participants assigned to the *SP* condition will be offered the opportunity to participate in a *SAH-C* group. This participation would be entirely voluntary and would involve no further assessment or remuneration.

(6) Measures

(a) Outcome Measures

Outcome assessments are identical to those from Phase 1, though the assessment window for Phase 2 assessments refers to the prior three months. Data collected will include demographics questionnaire, partner contact form, PCL, AUDIT, Post-Intervention satisfaction, suicidality measure, MMEA⁸⁰, CTS2⁴⁴, ongoing intervention questionnaire, and DAS⁶⁹.

(b) Intervention Compliance Measure

Session Attendance will be measured as the total number of group sessions attended by each client.

(7) Stakeholder Meetings

Stakeholder meetings will be held to discuss study performance and needs of the study, such as discussions related to study recruitment, barriers to participation, and dissemination of research findings.

(c) Intent-to-Treat (ITT) versus “Adequate Dose” Analyses

An ITT philosophy will be strictly adopted. Experts in clinical trials have noted that no consensus exists about how missing data should be handled in ITT analyses, and different imputation approaches result in various potential biases. Thus, there is no single definition of ITT, and the phrase carries different meanings for different researchers.^{87,88} Therefore, every effort will be made to collect complete outcome data for all randomized participants, regardless of their intervention completion. As discussed in section D.3.7., measurement losses are expected to be relatively small due primarily to the use of tracking procedures, as well as the relatively short follow-up assessment periods.

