Analyses will first be conducted on the ITT sample, and then on the subset of participants who are considered to have received an “adequate dose” of the group intervention over the course of the study. We intend to focus on a comparison of those who had an adequate dose versus completed the intervention, because the group sessions will continue in spite of a couple’s non-attendance. This approach is consistent with prior group interventions.⁸⁹ It is recognized that the ITT and adequate dose analyses address different questions, and only the ITT analyses permit strong inferences. However, there is important information to be gained in looking at the data both ways.

(d) Primary Data Analyses

Formal data analyses will be conducted only on those subjects recruited during Phase 2 of the project, as this is the only phase that includes random assignment. Differences between the *SAH-C* groups and *SP* groups on the frequency of physical and psychological IPA and relationship satisfaction (Aim 1) will be examined with random-effects regression models, using Hierarchical Linear Modeling (HLM5).⁹⁰ Random-effects regression models provide more flexibility in modeling missing data than general linear models. They do not require data to be missing completely at random, but only missing at random (that is, the probability of missingness is

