assumed to be a function of observed covariates and previously measured outcomes, but not unobserved outcomes). Based on such considerations, this type of an approach has been recommended for analyzing outcomes in prevention trials as it is generally more powerful than traditional repeated measures analyses of variance.⁹¹ In the current project it is of interest to model person-specific effects (i.e., time course for each participant), as well as the variation of responses between individuals. In addition, because of the suspected intraclass correlation between individuals nested within intervention groups, couples, and perhaps intervention site, these variables will be treated as fixed effects in the analyses. Time will be modeled as a random effect, and condition (*SAH-C* and *ST*) will be a fixed effect. Change in intervention outcomes over time and differences between the conditions over time (intervention by time interactions) will be examined. The primary effect size for the study will be derived from the random regression analyses, and specifically the intervention by time interaction, which will compare the two groups across intervention and follow ups. There are covariates that are *a priori* hypothesized to be associated with intervention outcomes, including socioeconomic status and education, and these will be included in follow-up analyses to significantly reduce error variance.

(e) Exploratory Analyses

Differences between the two group conditions in participant intervention compliance (Aim 2) will be explored by examining condition differences in session attendance using ANOVAs.

(f) Qualitative Analytic Strategy and Data Integration

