Our first consideration in estimating the necessary sample size for detecting differential change over time in *SAH-C* versus *SP* in terms of IPA incidence was the expected incidence rate of IPA during the follow-up period. Our sample is at high risk for such incidence as defined by the presence of high levels of marital distress. While there is no prospective military data available that directly speaks to such incidence rates, available estimates suggest a 33% one-year prevalence of IPA among trauma exposed service members.⁹³ Conservatively, it would be expected that during the current project, approximately 16% of cases of IPA would emerge (half of the one year prevalence). However, inclusion of only couples with high levels of marital distress will increase this estimated incidence rate. Accordingly, we expect an increase of 10% in the incidence rate. Together, we based power analyses on an estimated 26% one-year incidence rate. Our second consideration involved expected sample attrition. Based on our prior trial and the specific plan for data capture outlined for the project, we estimate that about 15% of participants will provide no follow-up assessment data. However, power analyses were conducted based on the conservative estimate of 20% assessment dropout. Consistent with an ITT approach, regardless of intervention dropout, we will assess participants randomized into the trial. Thus, dropout from measurement versus intervention is of greatest concern. Our third consideration involved expected within-subjects correlations. The within-subjects correlation was estimated as the average correlation observed in our previous trial for pre-intervention, post-intervention, and follow-up data on reports of physical and psychological IPA on the Revised Conflict Tactics Scale (CTS-2).⁴⁴ These correlations ranged from .53 to .90. We also considered the expected intra-class (group) correlation, which was approximately .05. Finally, consistent with recommendations,⁹⁴ we considered the intra-class (dyadic) correlation among couples. We did not incorporate an estimate of such correlations into power analyses because of our proposed use of a composite measure of IPA, which results in a single index of IPA, thereby eliminating intra-dyad correlations. Together, we assumed an intra-class correlation of .38 for power analyses. Our fifth consideration involved the expected effect size of the *SAH-C* relative to *ST*. Our prior work suggested an ITT effect size of $d = 1.01$. A conservative estimate of a mean effect size of $d = .5$ for the *SAH-C* in terms of reduction of IPA incidence was utilized for the power analysis.

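### The exploratory Aim 2 attendance ANOVA has no term for couple or intervention group, so its standard error is too small if attendance is positively correlated within either

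*Combined protocol and SAP*

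**What the plan says.** All references are to the combined protocol and SAP.

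- **Aim.** Section (1)(c), Specific Objectives, gives Aim 2 as: "To explore differences in compliance factors across conditions, we will compare session attendance".
- **Measure.** Section (6)(b), Intervention Compliance Measure: "Session Attendance will be measured as the total number of group sessions attended by each client".
- **Analysis.** Section (e), Exploratory Analyses, says the differences "will be explored by examining condition differences in session attendance using ANOVAs". No couple term, group term, unit of analysis or significance level is given.
- **Delivery.** Section (5)(c), Interventions: "In total, 28 intervention groups will be conducted (14 for each condition), with five couples per group". Section (2)(c) gives a reason for this format: "A group couples format is used because group cohesion among clients appears to be associated with IPA prevention".
- **Clustering elsewhere.** Section (d), Primary Data Analyses, names correlation within intervention groups and within couples, but only for the Aim 1 models. Section (g), Power Analysis, refers to the "expected intra-class (group) correlation, which was approximately .05" for the aggression outcomes. It sets the dyadic correlation aside because those outcomes are combined into one index per couple. No such index is defined for attendance.

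**The concern.** Both members of a couple are in the same condition, and so are all five couples in a group. If partners tend to attend or miss sessions together, or if whole groups attend well or badly, the records carry less information about the condition difference than their number suggests. An ordinary ANOVA takes its error term from the spread of individual records and does not allow for this. Positive correlation at either level makes the standard error too small, the interval too narrow and the p-value too low.

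Aim 2 is one of three numbered aims, and attendance is its only named measure. In a hybrid effectiveness and implementation trial, a statement that one condition keeps couples attending better would feed into decisions about wider use. An overstated p-value could produce that statement by chance.

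**Working it through.** **Inputs from the documents.** 28 groups × 5 couples = 140 couples, and 140 × 2 = 280 people, which agrees with the total in Power Analysis. That is 10 people per group and 14 groups per condition. The group intraclass correlation is about .05, stated for aggression outcomes.

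**Inputs assumed.** The group correlation of .05 carries over to attendance. The test is two-sided at .05; the plan gives no level for Aim 2. The partner correlation in attendance, r, is nowhere stated, so it is varied from .05 (no couple effect beyond the group effect) to 1.0. The plan states no error rate or power for Aim 2, so there is no figure of its own to reproduce.

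**Case A: all 280 people pooled in one ANOVA.** Each person has one partner (correlation r) and eight other group members (correlation ICC):

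- design effect = 1 + r + 8 × ICC
- true type I error = 2 × [1 − Φ(1.96 / √design effect)]

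For r = .8 and ICC = .05, the design effect is 1 + .8 + .4 = 2.20. Then 1.96 / √2.20 = 1.32, and the type I error is .186. The last column is a simulation of 28 groups × 5 couples × 2 people, with 20,000 runs per row.

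| r (ICC = .05) | Design effect | Type I error | Multiple of .05 | Simulated |
|---|---|---|---|---|
| .05 | 1.45 | .104 | 2.1 | .104 |
| .38 | 1.78 | .142 | 2.8 | .137 |
| .5 | 1.90 | .155 | 3.1 | .154 |
| .8 | 2.20 | .186 | 3.7 | .193 |
| .9 | 2.30 | .196 | 3.9 | .199 |
| 1.0 | 2.40 | .206 | 4.1 | .208 |

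The value .38 appears in Power Analysis as an intraclass correlation of unexplained origin. It serves here only as an intermediate point.

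For r from .5 to 1.0 the naive standard error is too small by 1 − 1/√1.90 = 27% to 1 − 1/√2.40 = 35%. Correct intervals would be √1.90 = 1.38 to √2.40 = 1.55 times as wide.

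**Sensitivity to the group correlation (people pooled).**

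- ICC = 0: r = .8, .9 and 1.0 give design effects of 1.8, 1.9 and 2.0, and type I errors of .144, .155 and .166.
- ICC = .10: r = .8 and 1.0 give 2.6 and 2.8, and .224 and .241.
- Both correlations zero: no inflation.

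**Case B: one record per couple, or separate ANOVAs for service members and partners.** Each group then contributes five records and the partner correlation drops out:

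- design effect = 1 + 4 × .05 = 1.20
- type I error = 2 × [1 − Φ(1.96 / √1.20)] = .074, about 1.5 times nominal

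This takes .05 as the correlation of the record analysed. If .05 is the person-level value and the two partners' counts are averaged, the simulated error is .076 to .081 for r of .38 or more, and .097 at r = .05. With ICC = 0 there is no inflation in this case.

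**After correction.** A test of condition on the 28 group means (28 − 2 = 26 degrees of freedom) gave simulated type I errors of .046 to .052 across the settings tried.

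**The case against.** The strongest case on the other side has four parts.

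1. **The unit of analysis is not fixed.** The plan says how attendance is recorded, not that partners are pooled. The plural ANOVAs could mean one per role. In explaining the adequate-dose subset, the plan describes missed sessions as something a couple does ("because the group sessions will continue in spite of a couple", the sentence going on to non-attendance), which could point to one record per couple. A nested ANOVA is not excluded either. This stands and lowers the lower end of the range. The group-level correlation remains under the first two readings, and nothing in the text specifies a nested analysis.

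2. **The partner correlation is not in the documents.** A reader might infer that partners' counts are practically one number entered twice, and hence that the false-positive rate is simply three to four times nominal. The documents do not support that as a fixed result. No correlation is given, and the early-termination rule in section (5)(e) is written for participants, not couples, so partners' counts can diverge. A high value is plausible because the format is built on couples attending together, but it is an assumption.

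3. **The group value of .05 belongs to another outcome.** This also stands. Attendance could cluster more or less strongly than aggression.

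4. **Aim 2 is exploratory.** No hypothesis, significance level or power is attached to it, and the primary hypotheses concern aggression and relationship satisfaction. That lowers the importance of the point. It does not make the standard error right.

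**Conclusion.** The concern holds in direction, with a conditional size. As written, the Aim 2 analysis includes neither level of clustering, and its standard error is too small whenever attendance is positively correlated within couples or groups.

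If a group correlation of .05 applies to attendance and the test is two-sided at .05:

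- one record per couple, or separate ANOVAs by role: about 7%, or 1.5 times nominal, and somewhat more if weakly correlated partners are averaged;
- all 280 people pooled: about 10% to 21%, or 2 to 4 times nominal, for partner correlations from .05 to 1.0, and 3 to 4 times only if that correlation is .5 or higher.

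With no group correlation and people pooled, it is 14% to 17% for partner correlations of .8 to 1.0.

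A reader might also infer that the trial's main findings are at risk. They are not: this point concerns Aim 2 alone. It should be corrected because the stated method gives a wrong error term and the correction is cheap.

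**What to change.** In Exploratory Analyses, replace the ANOVA with a mixed model of per-person attendance. Condition should be a fixed effect, couple and intervention group random effects, and the degrees of freedom a small-sample approximation based on the 28 groups. An equivalent and simpler choice is to test condition on the 28 group means with 26 degrees of freedom. State the unit of analysis either way.

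The group and couple terms need to be random. Condition does not vary within a group or couple, so entering those as fixed effects would leave nothing from which to estimate the condition difference in attendance.

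The cost is a few lines of analysis text. No further data, participants or visits are needed. The downside is wider Aim 2 intervals.
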